5.5. Dosing Regimen

Patients will receive one to four consecutive cycles of blinatumomab. A cycle consists of a continuous intravenous infusion at a dose of 28 mcg/day over four weeks followed by an infusion free interval of two weeks. Patients will receive four cycles of treatment, unless criteria for treatment discontinuation apply. The duration of one cycle is 6 weeks, including a four week continuous intravenous infusion and a two week infusion free interval, which may be extended by a maximum of 7 days. In case of haematological relapse, the study treatment will be permanently discontinued. Patients are generally are expected to receive four cycles of treatment, independently from achieving complete molecular response. If patients are suitable for allogeneic HSCT after treatment with at least one treatment cycle of blinatumomab, they may undergo allogeneic HSCT instead of receiving further cycles with blinatumomab. Following the last treatment cycle, there will be a safety follow-up visit at 90 days after last infusion, documented as End-of-Core-Study Visit, followed by efficacy follow-up visits at three, six, nine, 12, 18 and 24 months after treatment start. Efficacy follow-up visits at six months will only be applicable for patients completing less than 4 cycles, at three months only for patients having completed 1 cycle only.

After completion of the two year efficacy follow-up period, information concerning haematological relapse free, leukaemia treatment free and overall survival as well as further data on hospitalisation and the use of relevant anti-leukemic, antibiotic, and antifungal medication and transfusion of blood products, and hospitalisation, if available, will be gathered by telephone at least every six months until death or at least until five years after treatment start, whichever occurs earlier. Patients who discontinue treatment prematurely

will enter immediately the efficacy and/or survival follow-up study. Patients who discontinue treatment before completion of the first treatment cycle will be assessed for MRD response on day 29 (and day 43, if applicable) of cycle 1 before entering the efficacy and/or survival follow-up study. In case of haematological relapse within the treatment period, treatment will be terminated at the time of relapse.

5.6. Administration

Blinatumomab will be administered as a continuous intravenous (CIV) infusion at a constant flow rate rate as specified on the prescription, via a low protein binding infusion line with 0.2 micron inline filter using a CADD Ambulatory Infusion Pump. The infusion is for four weeks followed by a two-week infusion free interval, which may be prolonged for up to seven more days, if deemed necessary. There should be no planned interruptions in the infusion, e.g. for i.v. administration of other medication. Patients will be hospitalized during at least the first three days after start of infusion of the first treatment cycle and during at least the first two days after start of infusion of subsequent cycles. After interruption of treatment for more than 4 hours, the infusion should be restarted in the hospital, under supervision of the investigator. After interruptions for up to 4 hours, the infusion can be continued without specific measures.

The CADD infusion bags will be prepared as either 72 hour or 96 hour infusions, with the bags being changed twice a week. To account for weekends and bank holidays, this will occur on Tuesdays and Fridays. Each cycle should being on a Tuesday.

The infusion rate of the 250mL bag depends on the duration of the infusion:

- 72 hour infusions: Administer at a constant infusion rate of 3.33 mL/h over 72 hours, to achieve a final infusion volume of 240 mL for each subject. Any remaining infusion solution volume present in the infusion lines must be discarded.
- 96 hour infusions: Administer at a constant infusion rate of 2.5 mL/h over 96 hours, to achieve a final infusion volume of 240 mL for each subject. Any remaining infusion solution volume present in the infusion lines must be discarded.

Problems with the infusion bag, pump, or intravenous access should be rectified as soon as possible by contacting the Acute Oncology Service on [name]

5.7. Treatment Interruptions/Dose modification for toxicity

For all patients consideration to discontinue blinatumomab temporarily or permanently as appropriate should be made in the case of the following severe (grade 3) or life-threatening (grade 4) toxicities: cytokine release syndrome, tumour lysis syndrome, neurological toxicity, elevated liver enzymes and any other clinically relevant toxicities. If the interruption of treatment after an adverse event is no longer than 7 days, continue the same cycle to a total of 28 days of infusion inclusive of days before and after the interruption in that cycle. If an interruption due to an adverse event is longer than 7 days, start a new cycle. If the toxicity takes more than 14 days to resolve, discontinue therapy permanently.

5.8. IMP Risks

In case of any clinical/laboratory adverse event considered being medically relevant treatment may be interrupted or permanently discontinued at the discretion of the investigator. All treatment interruptions except for regular infusion bag changes will be documented clearly and concisely in the electronic medical record before being recorded with electronic Case Report Forms. Infusion bag changes, however, need to be documented in the patient's file.

Expectedness of SAEs is based on the Reference Safety Information listed in Appendix B of the Blinatumomab Investigators Brochure 2019.

Further information on the management of adverse events, including instructions on interruption of blinatumomab and supportive care, is included in the Appendix.

5.9. Criteria for Treatment Discontinuation

Treatment with blinatumomab will be discontinued in the event of any of the following:

- Haematological or extramedullary relapse
- Confirmed molecular progression between cycles (>1 log rise)
- Investigator's decision that a change of therapy is in the patient's best interest
- Patient or investigator not compliant with the study protocol
- Progression of a medical condition which in the opinion of the investigator should lead to treatment discontinuation
- Administration of relevant non-permitted concomitant medication(s)
- Occurrence of an adverse event which makes discontinuation from treatment desirable or necessary in the investigator's and/or the patient's opinion
- Infusion interruption of more than two weeks due to AE
- Central laboratory determination that the patient's screening bone marrow demonstrates that the patient was ineligible for study treatment due to MRD negativity at the time of enrolment.
- Occurrence of toxicities as described in the Appendix

5.10. Patient Monitoring

The patient is to be an in-patient during the first two days of each treatment cycle (three days of the first cycle) because of potential side effects associated with T cell redistribution and potential cytokine release effects triggered by the administration of blinatumomab. Nurses and physicians trained in management of medical emergencies should be available for immediate intervention in case of complications.

5.11. Out-patient Treatment

Blinatumomab will be administered on an in-patient basis during at least the first three days after start of infusion of the first treatment cycle and during at least the first two days after start of infusion of each following cycle or if necessary for restart of treatment following temporary discontinuations due to adverse events. Afterwards the treatment will be continued on an out-patient basis, if it seems to be safe and feasible to the investigator. For the approval of an out-patient treatment the following conditions will have to be met:

- The patient will be able and willing to visit the investigator at the study centre
 according to the study visit schedule, which is weekly during the infusion period
 assuring infusion bag change, monitoring of vital signs, and
 monitoring/documentation of AE/SAE.
- In addition, regular visits to the study site infusion centre by the patient for review by a well-trained nurse or medical doctor being thoroughly familiar with the study will be guaranteed assuring infusion bag change, maintenance of port, and, monitoring of vital signs.
- A continuous ambulatory drug delivery (CADD) pump will monitor delivery of the IMP.

5.12. Management of overdose

Overdoses have been observed including one patient who received 133-fold the recommended therapeutic dose delivered over a short duration. Overdoses resulted in adverse reactions which were consistent with the reactions observed at the recommended therapeutic dose and included fever, tremors, and headache. In the event of overdose, the infusion should be temporarily interrupted and patients should be monitored. Re-initiation of blinatumomab at the correct therapeutic dose should be considered when all toxicities have resolved and no earlier than 12 hours after interruption of the infusion. Overdose, with or without any signs or symptoms, will be handled and reported as a serious adverse event (SAE).

5.13. Premedication

The clinical experience with blinatumomab has resulted in implementation of a premedication regimen described below:

Obligatory Pre-Medication:

- In adult patients, dexamethasone 20 mg intravenous should be administered 1 hour prior to initiation of each cycle of blinatumomab.
- Anti-pyretic use (e.g. paracetamol) is recommended to reduce pyrexia during the first 48 hours of each treatment cycle

During the treatment period:

In case of CNS-related events dexamethasone should be administered orally at a dose of at least 24 mg per day for up to three days. The dose will then be step-wise reduced over up to four days. If the CNS event was a seizure, appropriate prophylactic anticonvulsant treatment with a therapeutic dose of e.g. phenytoin or levetiracetam will be administered during restart and during start of the following new treatment cycle. For further information see Appendix.

5.14. Concomitant Medication

The following medication and therapies will be prohibited during the study until end of the efficacy period:

- Any anti-tumour therapy other than the investigational product i.e. cytotoxic and/or cytostatic drugs, radiation therapy or immunotherapy.
- Any other investigational agent
- Chronic systemic high-dose corticosteroid therapy (i. e. > 20 mg prednisone daily)
- Any other immunosuppressive therapies (except for protocol mandated interventional corticosteroids)
- Non-steroidal anti-inflammatory drugs (NSAIDs, except for paracetamol and naproxen)
- Tyrosine kinase inhibitors

For management of concomitant therapies, please refer to the Investigators Brochure. A complete listing of all concomitant medication received during the treatment phase must be recorded in the relevant CRF. This will include all medications at baseline and any changes during the treatment period.

6. Selection and Withdrawal of Participants

6.1. Inclusion Criteria

Participants are eligible for the trial if they meet all of the following inclusion criteria and none of the exclusion criteria apply. All queries about participant eligibility should be directed to

the Trial Manager before randomisation/registration and no eligibility wavers will be permitted.

- 1) Patients with AML with a t(8:21) translocation in complete haematological remission (defined as less than 5% blasts in bone marrow) with a confirmed first or subsequent molecular relapse or molecular persistence of disease (defined according to European Leukaemia Net criteria) following remission induction therapy comprising 2 courses of an anthracycline based regimen or one course of an anthracycline based regimen plus a second course of high dose cytarabine (HDAC).
- 2) Bone marrow or peripheral blood specimen from primary AML sample taken at diagnosis documented as showing expression of CD19.
- 3) Bone marrow function as defined below:
 - Neutrophils $>1x10^9/L$ Platelets $> 20 \times 10^{12}/L$ (transfusion permitted)
 - Haemoglobin level >9g/dl (transfusion permitted)
- 4) Renal and hepatic function as defined below:
 - AST , ALT , and ALP < 2 x upper limit of normal (ULN) Total bilirubin < 1.5 x ULN
 - Creatinine clearance >50 mL/min (calculated according Cockroft & Gault)
- 5) Negative HIV antibody test, negative hepatitis B (HbsAg) and hepatitis C virus (anti-HCV) test with the exception of well controlled chronic infections with at least two documented undetected PCR tests for viral load.
- 6) Negative highly sensitive pregnancy test in women of childbearing
- 7) ECOG Performance Status 0 2.
- 8) Age 18 years or older
- 9) Ability to understand and willingness to provide written informed consent.

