Endpoints	Primary – incidence of molecular complete remission after one cycle of treatment.
	 Secondary: Incidence of patients experiencing a grade 3 or greater non-haematological toxicity during the first cycle of treatment. Incidence of molecular complete remission at any time from trial entry Molecular relapse free survival time Overall survival time Number of days of hospital admission at 1, 3 and 6 months from entry Number of days on intravenous antibiotics or antifungals at 1, 3 and 6 months

	 Number of blood components infused at 1, 3 and 6 months.
Sample size	17 patients in total, comprising 7 in Stage I and 10 in Stage II
Summary of eligibility criteria	Confirmed first or subsequent molecular relapse or molecular persistence of AML with t(8;21) following remission induction therapy Documented CD19 expression on blasts at diagnosis or relapse. Adequate bone marrow function Age 18years or older Excluding patients with >5% blasts in BM or evidence of extramedullary relapse. Weight 45kg or greater
IMP, dosage and route of administration	Blinatumomab at 28 mcg/day per day by continuous infusion for 28 days for up to 4 cycles of therapy.
Active comparator product(s)	N/A
Maximum duration of treatment of a participant	4 cycles of 28 days each
Version and date of protocol amendments	

2. Glossary of Terms

ABPI Association of the British Pharmaceutical Industry

AE Adverse Event

ALL Acute lymphoblastic leukaemiae

ALP Alkaline phosphatase
ALT Alanine transaminase
AML Acute myeloid leukaemia

AR Adverse Reaction
AST Aspartate transaminase
BiTE Bispecific T-cell engagers
CA Competent Authority

CADD Continuous ambulatory drug delivery

CI Chief Investigator
CIV Continuous intravenous
CNS Central nervous system
CR Complete remission
CRF Case Report Form
CRP C-reactive protein

CRS Cytokine release syndrome CTA Clinical Trial Authorisation

CTCAE Common Terminology Criteria for Adverse Events

CTFG Clinical Trials Facilitation Group

CTO Clinical Trials Office

DSUR Development Safety Update Report

ECG Electrocardiogram

ECOG Eastern Cooperative Oncology Group

eCRF Electronic case report form
EEA European Economic Area
EMR Electronic medical record

EudraCT European Clinical Trials Database

FBC Full blood count GCP Good Clinical Practice

GMP Good Manufacturing Practice

HBV Hepatitis B virus

HCG Human chorionic gonadotropin

HCV Hepatitis C virus
HDAC High dose cytarabine

HIV Human immuno-deficiency virus

HSCT Haematopoietic stem cell transplantation

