7.1.2. Eligibility Assessments

The following procedures and assessments must be performed during the screening period within three weeks prior to the first administration of the investigational product (Day 1):

Inclusion/Exclusion

Assessment of the patient's eligibility will be performed as outlined in section 6, including review of all laboratory measurements performed during the screening period. Eligibility will also need to be confirmed at treatment initiation.

Demographics

Date of birth, sex and ethnic origin will be recorded at screening.

Medical History/Current Medical Conditions

General and disease specific medical history including a history of past and current medical conditions, full history of the course of the patient's leukaemia including immunophenotype, karyotype, molecular phenotype, data on disease subset specifics, information on prior antitumour therapies and current eligibility for HSCT will be recorded at screening.

Physical Examination

Comprehensive physical examinations of all body systems will be performed at the screening visit.

Neurological Examination

During the screening visit a neurological examination will be performed including the test of the following functions: level of consciousness, orientation, vision, cranial nerves and brain stem functions, pyramidal and extrapyramidal motor system, reflexes, muscle tone and trophic findings, coordination, sensory system, neuropsychological findings (e.g., speech, cognition and emotion).

Writing Test

Patients will be asked to perform a writing test at screeningt in order to monitor patients for the onset and resolution of writing difficulties which may be an indicator for neurological AEs.

ECOG Performance Status

The patient's performance status will be assessed at screening using the Eastern Cooperative Oncology Group (ECOG) score.

Vital Signs

Body temperature, heart rate and blood pressure (systolic/diastolic) will be measured during screening

Electrocardiogram (ECG)

Standard 12-lead ECG will be performed at screening.

Blood tests

Blood samples for laboratory evaluations will be taken at screening. The following analyses will be performed:

- Serum chemistry
- Glucose, sodium, urea, uric acid, potassium, calcium, magnesium, phosphate, chloride, creatinine, total bilirubin, alkaline phosphatase (ALP), aspartate transaminase (AST), alanine transaminase (ALT), total serum protein, albumin, lactic dehydrogenase (LDH), C-reactive protein (CRP).
- Full blood count

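### Inclusion criterion 3 prints a platelet floor of more than 20 x 10^12/L, which cannot be applied as written, and no other part of the protocol states the limit

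*Protocol*

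**What the plan says.** Inclusion criterion 3 in section 6.1 sets limits for bone marrow function. The neutrophil limit is "Neutrophils $>1x10^9/L". The platelet limit is "Platelets $> 20 \times 10^{12}/L$ (transfusion permitted". A haemoglobin limit follows, also with transfusion allowed.

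The limits are binding. The section opens with "Participants are eligible for the trial if they meet all of the following inclusion criteria and none of the exclusion criteria apply" and adds that "no eligibility wavers will be permitted". Section 7.1.2 has eligibility assessed against section 6, "including review of all laboratory measurements performed during the screening period", and confirmed again when treatment starts.

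The only other mention of marrow function as an entry requirement is in the synopsis, "Adequate bone marrow function", with no number. The exclusion criteria in section 6.2 contain no platelet limit.

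**The concern.** The neutrophil and platelet limits stand in one criterion but in units that differ by a factor of 1,000, and the platelet figure is outside anything a blood count can return. The allowance for transfusion shows that the authors meant a low floor, one that some patients might need support to reach. The printed number cannot be such a floor.

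At stake is whether this entry criterion can be applied and audited. A numeric limit that cannot be met, with no waiver route and no second statement of it, leaves two outcomes. Either the site enrols against a limit that is not in the protocol, or each enrolled patient is logged as an eligibility deviation on this item. In both cases a later reader cannot tell from the protocol which platelet counts were admissible.

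**Working it through.** **Inputs from the protocol**
- Platelet floor: more than 20 x 10^12/L, transfusion allowed (section 6.1, criterion 3).
- Neutrophil floor: more than 1 x 10^9/L (same criterion).
- All criteria required, no waivers (section 6.1).
- Synopsis: no number for marrow function.
- Design: "17 patients in total, comprising 7 in Stage I and 10 in Stage II"; continue with at least 4 responses of 7, success with at least 11 of 17; 50% against 75%; 15% significance level and 85% power (sections 4.4 and 10.1).

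**Assumptions, because the protocol gives no platelet reference range**
- Upper limit of normal: 400 to 450 x 10^9/L.
- Extreme high count: 1,000 to 2,000 x 10^9/L.

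**Step 1: convert the printed limit**
- 20 x 10^12/L ÷ 10^9/L = 20,000, so the floor is 20,000 x 10^9/L.
- Per microlitre: 20 x 10^12 ÷ 10^6 = 20,000,000.
- Ratio of the two units in the criterion: 10^12 ÷ 10^9 = 1,000.

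**Step 2: compare with possible counts**
- 20,000 ÷ 450 = 44.4 and 20,000 ÷ 400 = 50, so 44 to 50 times the assumed upper normal limit.
- 20,000 ÷ 2,000 = 10 and 20,000 ÷ 1,000 = 20, so 10 to 20 times the assumed extreme count.

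The result is the same at every point of both ranges: the floor cannot be reached.

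**Step 3: look for a second statement of the limit**
The synopsis has words without a number, section 6.2 has no platelet item, and section 7.1.2 refers back to section 6. The protocol therefore cannot be used to correct its own figure.

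**Step 4: check that the design is untouched**
The probability of declaring success at true response rate p is the sum, over x = 4 to 7, of P(Bin(7, p) = x) × P(Bin(10, p) ≥ 11 − x).

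At p = 0.50 this is (35 × 176 + 21 × 386 + 7 × 638 + 1 × 848) ÷ (128 × 1,024) = 19,580 ÷ 131,072 = 0.149. At p = 0.75 the same sum gives 0.860.

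Both agree with the stated 15% and 85%. The platelet limit does not enter this calculation. Nor does it enter the primary endpoint, which is absence of detectable fusion transcript after cycle 1 (sections 4.2 and 8.1).

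**The case against.** The strongest reply is that this is an evident misprint which would mislead no haematologist. Section 6.1 sends eligibility queries to the Trial Manager before registration. Section 6.8 has one site in the first stage and at most two more, added by amendment, in the second. A rule against waivers stops ineligible patients from being enrolled; it does not stop a misprinted unit from being clarified. The neutrophil, haemoglobin, renal, hepatic and performance-status limits are still stated. Most of this stands, and it limits the practical harm. It does not supply the missing number: a central answer to a query would still be a limit that the protocol does not contain.

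A second reply is that the exponent may have been misread when the PDF was converted to text. Some symbols elsewhere were damaged: the range in the performance-status criterion has lost its dash, and the hypothesis notation in section 10.1 is garbled. This cannot be excluded. The neighbouring exponent 9 came through correctly and 12 is a well-formed two-digit exponent, so a reading error is less likely but still possible. The original page has to be checked first.

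A reader might infer more: that nobody can be enrolled, that each assessor must guess separately, or that the trial's statistics are compromised. The first holds only on a literal reading that no one is likely to apply. The second does not fit the central query route and the single site in stage I. The third is contradicted by Step 4 of the working, and section 10.2 defines its analysis set by receipt of at least one dose, so a deviation on this item would not by itself remove anyone.

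**Conclusion.** The point holds as an error in a binding entry criterion. The printed floor of 20,000 x 10^9/L is 44 to 50 times an assumed upper normal limit and 10 to 20 times an assumed extreme count. It is inconsistent with its own transfusion allowance, and nothing else in the protocol corrects it. As written, criterion 3 cannot be applied.

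The probable cause is a misprint in the exponent or the unit, and the realistic consequence is enrolment against an unwritten limit or deviations on paper. There is no effect on sample size, type I error, power or the primary endpoint.

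The conclusion rests on the exponent being printed as it was read, and on the assumed platelet ranges, which would have to be wrong by at least a factor of 10 to change it. The 1,000-fold difference between the units does not show that 20 is the right number with only the exponent wrong. The protocol does not establish the intended limit.

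**What to change.** Check the exponent in criterion 3 against the original page. If it is printed as read, the sponsor or chief investigator should confirm both the intended platelet limit and its unit, and criterion 3 should be corrected. Any eligibility form or data-entry check built from the criterion should be compared with the corrected text; those documents are not available here, so whether they need changing is unknown. The synopsis has no platelet figure and needs no change on this account. This review proposes no value.

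The cost is one confirmed figure and unit in section 6.1, made through a protocol amendment, and one comparison of any check derived from it. The design and the analysis stay as they are.
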